Suvorexant for Opioid/Stimulant Co-use

NCT05546515

9/19/2024

JHM IRB - eForm A – Protocol

- Use the section headings to write the JHM IRB eForm A, inserting the appropriate material in each. If a section is not applicable, leave heading in and insert N/A.
- When submitting JHM IRB eForm A (new or revised), enter the date submitted to the field at the top of JHM IRB eForm A.

1. Abstract

The opioid epidemic has led to an unprecedented rise in opioid use disorder (OUD) cases and overdose deaths. In recent years, these increases have been accompanied by a rise in opioid/stimulant co-use, an issue that has existed for decades and for which no effective treatment has ever been identified. Current increases in opioid overdose deaths are now largely driven by stimulant co-use. Thus, innovative treatments that are safe and effective among patients co-using opioids and stimulants are urgently needed. Suvorexant (SUVO) is an FDA-approved medication used to treat insomnia. SUVO interacts with the brains reward system in such a way that it may reduce craving for stimulants in persons using opioids, and we recently also found that SUVO reduced craving and increased total sleep time among individuals who were withdrawing from opioids. That study also showed that SUVO was extremely safe and well-tolerated in persons using opioids.

This between-subjects, double-blinded, randomized controlled pilot study will recruit patients who are receiving methadone or buprenorphine treatment for OUD and are using cocaine. Participants will be randomly assigned to receive 28-30-days of SUVO or placebo. They will visit the clinic regularly to provide urine drug screens and complete questionnaires and will wear a device that can measure their sleep parameters. We expect that relative to persons who receive placebo, individuals who receive SUVO will 1) be less likely to screen positive for cocaine and/or opioids on urine drug screens, 2) will report lower drug craving, 3) will have better sleep continuity (i.e., longer total sleep time, shorter wake after sleep onset, and greater self-reported sleep quality, and 4) will report overall lower stress and better mood than persons who receive placebo. We also expect that patients will not have side effects from SUVO. These preliminary data will inform whether this FDA-approved medication may help patients stop co-using opioids and stimulants, which can be scaled up to reduce public health consequences related to co-use.

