Study Overview: Participants who are in methadone or buprenorphine treatment for OUD and are using cocaine will be recruited from the community to visit the clinic twice weekly and provide urine tests that will be analyzed for evidence of recent drug use and complete self-reported measures. All participants will be randomized to receive double-blinded doses of suvorexant (20mg, oral, QD) or placebo, which will be dispensed in blister packages for 28-30 days. Medication will be over-encapsulated and will include either 10mg SUVO or placebo. Participants will be expected to take 2 capsules each night and will be informed they can reduce their dose to 1 capsule per night if desired (these data will be documented as a secondary outcome).

Recruitment: Participants will be recruited from the community using social media advertisements, flyers, and newspaper advertisements. Recruitment will also include review of clinical records of individuals who are not clinical patients of the PI or co-investigators prior to their consent at Man Alive. At ATS, recruitment will include referral of individuals specifically for research purposes by treating clinicians not on the study team and recruitment of individuals who are patients of the study co-investigators. Interested individuals will complete a brief screening to determine initial eligibility before completing a full eligibility screen.

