Screening visit(s). Screening procedures may be scheduled across more than 1 day to meet participant schedules. Prior to completing any study-related screening, participants will review and sign an informed consent form with a trained staff member. Participants will be given the opportunity to do an in-person or a remote consent. For participants that complete the remote consent, some screening procedures will also be completed remotely, including interviews and questionnaires. Participants who complete this initial eligibility screening will complete the remainder of their screening visit in person. During the screening visit, participants will be assessed for inclusion and exclusion criteria. A urine drug-screen will be collected to assess for recent drug exposure and pregnancy (when indicated), the Mini-International Neuropsychiatric Interview (M.I.N.I.), the Addiction Severity Index (McLellan, Cacciola, & Zanis, 1997), the Columbia Suicide Severity Rating Scale, a demographic questionnaire, and a health form assessing current conditions and medications will be used to help evaluate participant eligibility.

Baseline/Randomization visit. Following determination of eligibility, participants will be randomized (stratified by gender) to receive 20mg of SUVO (the maximum FDA approved dose) or placebo. Randomization will occur prior to visit 1. At the randomization visit, participants will provide a urine sample that will be tested for recent drug use and complete self-report measures as described below. They may also complete a cue-induced craving paradigm, a probabilistic reward task, and the Trier Social Stress Test (TSST) described below. Participants will also be provided with an actigraph-like device to wear for the duration of their study participation to assess sleep.

Medication dispensing will begin during the baseline session. Participants will receive a blister package with 7-days of medication dispensed as two capsules (10mg SUVO or placebo) so that medication doses can be reduced to 50% of the dose if requested by a

Date: 09/19/2024

Principal Investigator: [name].

Application Number: IRB00341328

participant. Participants will also receive a 3-day blister package as a contingency strategy in case of missed visits. Participants will be instructed to return blister packages once weekly as a measure of medication compliance.

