Participants will be blinded to whether they received SUVO vs. placebo. This is meant to enhance study rigor and control for expectancy effects.

e. Justification of why participants will not receive routine care or will have current therapy stopped.

There is no current routine care for stimulant use disorder. Participants will not be removed from routine care and will continue participating in their treatment for OUD as indicated.

f. Justification for inclusion of a placebo or non-treatment group.

Inclusion of a placebo group will be necessary to determine if SUVO is efficacious in improving outcomes for patients receiving treatment for OUD and using cocaine.

g. Definition of treatment failure or participant removal criteria.

Participants will be removed from the study if they opt out or if the medical team determines it is not safe to continue in the study or if they request to discharge from the study. Participants who become pregnant, are incarcerated or hospitalized for ≥ 7 days, end their OUD treatment, or rescind consent/ask to be discharged will be removed from the study. Additional stopping rules will include not abiding by study policies and procedures, or engaging in behaviors towards staff or other participants that are abusive. Finally, development of an intercurrent illness or condition that changes the participant's risk profile may result in a medically-related discharge from the study.

Date: 09/19/2024

Principal Investigator: [name].

Application Number: IRB00341328

h. Description of what happens to participants receiving therapy when study ends or if a participant's participation in the study ends prematurely.

Participants will continue to receive their clinically-indicated care for OUD treatment.

Participants will be able to request a suvorexant prescription from their PCP if interested in continuing with the study medication after study completion.

i. If biological materials are involved, please describe all the experimental procedures and analyses in which they will be used.

Urine drug screens will be used as an outcome in this analysis. Urine drug screens will be taken at each visit using biochemical urine panel dip stick tests. The research coordinator will record the result of the urine drug screen. Urine specimens will be stored for future research.

5. Inclusion/Exclusion Criteria

Inclusion criteria:

- 1) Ages 18-65,
- 2) Meet DSM-5 criteria for stimulant use disorder,

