- 3) Currently receiving methadone or buprenorphine treatment for OUD and considered to be stable on current dose for at least 30 days;
- 4) Willingness to engage with study protocol,
- 5) Use of birth control (as appropriate),

Exclusion criteria:

- 1) Psychiatric or medical conditions that are judged by the investigators to interfere with participation or that are contraindicated for use with SUVO,
- 2) Pregnant or breastfeeding,
- 3) Current use of benzodiazepines, tranquilizers, or other schedule IV sleep medications,
- 4) Moderate or severe substance use disorder other than opioid, stimulant, or cannabis use disorder;
- 5) SUVO consumption in the last 30 days,
- 6) Use of medications that are contraindicated with the study;
- 7) Past 30-day suicidal behavior,
- 8) Use of continuous positive airway pressure (CPAP) device for sleep apnea.

6. Drugs/ Substances/ Devices

a. The rationale for choosing the drug and dose or for choosing the device to be used.

Suvorexant (SUVO) is a dual orexin receptor antagonist (DORA) and an FDA-approved medication for treating insomnia. The 20mg dose is the maximum approved dose for use by the FDA. Our recent study demonstrated that a dose of SUVO 20mg reduced craving, insomnia symptoms, and withdrawal in persons undergoing opioid withdrawal (Huhn et al., 2022). Other research groups have found SUVO can improve restful sleep and reduced wake after sleep onset among individuals using cocaine (Suchting et al., 2020). SUVO has a strong safety profile, low abuse liability, and dose not produce withdrawal symptoms after discontinuation (Huhn et al., 2022; Suchting et al., 2022; Herring et al., 2016). Importantly, SUVO is hypothesized to restore

Date: 09/19/2024

Principal Investigator: [name].

Application Number: IRB00341328

dopaminergic functioning, which we believe is disrupted in persons who are co-using opioids and stimulants and is the mechanistic reason we are evaluating SUVO in this study.

- b. Justification and safety information if FDA approved drugs will be administered for non-FDA approved indications or if doses or routes of administration or participant populations are changed.

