We are proposing to administer SUVO 20mg, which is an FDA-approved dose. We are not requiring insomnia as an inclusion criterion in order to focus more specifically on opioid-stimulant co-use behaviors. We have collected substantial evidence that SUVO is safe and does not increase risk of misuse in persons with OUD (see Huhn et al., 2022).

- c. Justification and safety information if non-FDA approved drugs without an IND will be administered.

SUVO is an FDA-approved medication. We are not submitting for an IND because the intervention is not intended to be reported to the FDA as a well-controlled study or for a significant label change, it is not intended to support a significant change in the advertising for the product, and it does not involve a route or dose level or patient population for which there is increased risk associated with use of the drug.

7. Study Statistics

- a. Primary outcome variable

Urine drug-screen results. Participants will complete a urine drug screen at each clinic visit. The presence or absence of non-prescribed opioids and/or cocaine will be recoded at twice-weekly sessions. The primary outcomes will be 1) the presence of absence of opioids at each screen, 2) the presence or absence of cocaine at each screen, and 3) the presence or absence of a screen that is negative for all illicit substances.

Self-reported opioid and cocaine craving. Participant will complete visual analogue scale measures of opioid and cocaine craving during each weekly visit. The average score across each visual analogue scale will be a primary outcome.

Opioid and cocaine cue reactivity. Participants will also complete visual analogue scales in the presence of drug cues. Average scores on visual analogue scales will serve as a primary outcome

- b. Secondary outcome variables.

Insomnia Severity Index Scores. The Insomnia Severity Index is a seven-item screening measure of insomnia. Items are rated on a five-point scale. A cut score of 15 is typically used to demarcate clinical insomnia. The scale has been shown to have excellent psychometric properties, including among patients with substance use disorders.

Sleep Continuity. Using actigraphy and sleep-diaries (in which persons will be asked to report on their sleep the night before the assessment), we will focus on three commonly used sleep continuity outcomes: 1) total sleep time (TST), or the total number of minutes that an individual

Date: 09/19/2024

Principal Investigator: [name].

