Application Number: IRB00341328

is asleep, 2) wake after sleep onset (WASO), or the total number of minutes that an individual is awake after sleep onset and prior to awakening, and 3) subjective sleep quality.

Co-occurring affective symptoms. Participants will be assessed for positive and negative affect using the PANAS. Participants will report perceived stress using the Perceived Stress Scale (PSS) is a 10-item measure of perceived stress. Items are rated on a five-point scale.

Abuse Liability Assessments (i.e., Medication Satisfaction Questionnaire). Participants will be asked to complete abuse liability measures. Participants will also be assessed for adverse events and serious adverse events in each visits. The abuse liability of the blinded study drug will be assessed by asking participants to rate “drug effects”, “good effects”, and “bad effects”, on a 0-100 point VAS, with 0 being “None” and 100 being “Extremely”. Participants will also report the perceived street value of the study drug. These subjective drug effect ratings are considered by the FDA to be the gold standard for assessing abuse liability.

Adverse events We will follow standard FDA guidelines regarding adverse events. Participants will be able to self-report adverse events via a study contact number. Events will be documented on a standardized form that adheres to FDA standards for adverse event reporting (e.g., event, system affected, start and stop date/time, perceived relationship to the study, severity, expectedness).

c. Statistical plan including sample size justification and interim data analysis.

Primary Aim 1. To examine whether SUVO 20mg reduces opioid and cocaine use and craving relative to placebo, a series of mixed models will be conducted. For analyses with a binary outcome (i.e., use at each assessment), generalized logistic models will be used, and for analyses with a continuous outcome (i.e., craving), linear mixed models will be used. Mixed effects models will also be used to compare drug cue reactivity at baseline and during the final week. For each model, we will include main effects of timepoint and medication group, as well as an interaction term. If the two treatment groups are systematically different on demographic or use characteristics at baseline, these measures will be included as covariates in the analysis. Models will involve a random intercept.

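### Entry does not require current non-prescribed opioid use, yet opioid use and craving are primary outcomes and the Aim 1 models make no planned use of opioid status at entry

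*Combined protocol and SAP*

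**What the plan says.** **Who enters.** Of the five inclusion criteria in section 5, one names a substance use disorder ("Meet DSM-5 criteria for stimulant use disorder") and one concerns opioids ("Currently receiving methadone or buprenorphine treatment for OUD and considered to be stable on current dose for at least 30 days"). Stability there describes the agonist dose. It neither requires nor excludes illicit opioid use. The abstract says the study "will recruit patients who are receiving methadone or buprenorphine treatment for OUD and are using cocaine", and the study overview in section 4a describes the same population. A urine drug screen is taken at screening and again at the randomisation visit (section 4a), but no opioid result is a condition of entry.

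**What is tested.** Section 7c states Primary Aim 1 as "To examine whether SUVO 20mg reduces opioid and cocaine use and craving relative to placebo". Section 7a lists "the presence of absence of opioids at each screen" first among the urine outcomes and also makes opioid craving and opioid cue reactivity primary. The abstract hopes to learn whether the drug "may help patients stop co-using opioids and stimulants".

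**How it is analysed.** Randomisation is stratified by gender only (section 4a). The Aim 1 models have time, group, their interaction and a random intercept. Demographic or use characteristics become covariates only if the arms are found to be systematically different at baseline, and no threshold is given (section 7c). Baseline is explicitly modelled for cue reactivity, which is compared between baseline and the final week. For urine screens and craving, the plan does not say whether baseline is one of the timepoints.

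**The concern.** A patient who takes no illicit opioids on a stable agonist dose but uses cocaine is eligible. In such a patient the opioid outcome can only record whether new use appears over about four weeks. In a patient using both drugs it records whether existing use falls. The planned models average the two, in proportions that nobody has set or predicted.

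Two things are at stake. First, the average opioid effect shrinks as the share of entry-negative patients grows, in a trial that has little power to spare. Second, a null opioid result could mean that the drug does not reduce opioid use, or that few participants were using opioids. As written, the analysis would not separate these readings, although the urine results that could do so are collected before the first dose.

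**Working it through.** **Inputs from the plan.** N = 40, two-sided alpha 0.05 (section 7c); 8 twice-weekly visits (section 4c).

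**Assumptions.** Equal allocation, so 20 per arm (the ratio is not stated). The share q of participants who are opioid-positive at entry is not given, so a range is shown. Users are taken to be positive on 80% of placebo and 40% of suvorexant screens.

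**1. The plan's own figure.** N = 40 is described as enough for a moderate-to-strong effect, with no effect size, power or SD, so it cannot be reproduced. Working back from 20 per arm for a single continuous measure at 80% power:

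d = (1.960 + 0.842) × √(2/20) = 0.89 (0.91 by t-test).

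Power is 34–35% for d = 0.5 and 69–72% for d = 0.8. Averaging 8 visits with a within-person correlation of 0.3 to 0.9 lowers the detectable d to 0.55–0.85. There is little slack before any dilution.

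**2. Dilution on one screen.** If entry-negative patients stay negative, the arm rates are 0.8q and 0.4q, and the difference is 0.4q. Power at 20 per arm is from the two-proportion normal approximation.

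| q | Rates | Difference | Power | N per arm for 80% power |
|---|---|---|---|---|
| 1 | 80% v 40% | 40 points | 75% | 23 |
| 0.75 | 60% v 30% | 30 points | 48% | 42 |
| 0.5 | 40% v 20% | 20 points | 28% | 82 |
| 0.25 | 20% v 10% | 10 points | 14% | 199 |

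**3. Eight visits.** Simulated share of positive screens per person, within-person correlation 0.5, t-test on person means (simpler than the planned mixed model). With no use of baseline status, power is 94%, 62%, 34% and 14% at q = 1, 0.75, 0.5 and 0.25. If entry-negative patients were positive on 20% of placebo and 10% of suvorexant screens, power at q = 0.5 is 51%: less loss, but still a loss.

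**4. What recovers the loss.** Same set-up, comparing a baseline-status covariate in all 40 with an analysis restricted to baseline-positive patients:

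| Entry-negative patients | Analysis | q = 0.3 | q = 0.5 | q = 0.6 |
|---|---|---|---|---|
| Stay negative | Covariate, all 40 | 41% | 64% | 74% |
| Stay negative | Restricted | 43% | 65% | 74% |
| 30% v 10% positive | Covariate, all 40 | 73% | 81% | 83% |
| 30% v 10% positive | Restricted | 43% | 66% | 76% |

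Repeat runs of the q = 0.5 case with negatives staying negative gave 65–69% for the covariate and 66–68% for restriction.

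A random-intercept logistic simulation, closer to the planned model (rates again assumed, q = 0.5, negatives staying negative), gave 44% with group only, 73% restricted, 82% with the covariate in all 40, and 82% for group-by-time with baseline as a modelled timepoint. Whether power is lost thus depends on whether baseline is modelled, which the plan leaves open for screens and craving.

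**5. Chance imbalance.** The SE of the arm difference in the share of users is √(2q(1−q)/20), or 14.5 points at q = 0.3 and 15.8 at q = 0.5. A difference of at least 4 participants arises by chance with probability 0.23 and 0.27 respectively. This is not an error rate. With no drug effect (users 80% positive, others 20%), the unadjusted test rejected in 4.5–5.0% of simulated trials at q = 0.3 to 0.6.

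**The case against.** The strongest reply is that the population is deliberate. The abstract, the study overview and the placebo justification in section 4f all describe patients in OUD treatment who use cocaine, and section 3 frames the question as cocaine co-use during agonist treatment. Analysing everyone randomised answers the opioid question for that population, and this is a 40-person pilot. That stands: the entry criteria are not an error, and all randomised participants belong in the primary analysis.

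Several stronger readings are tempting, and the documents do not support them:

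- *Entry-negative patients cannot benefit.* Aim 1 is about being less likely to test positive, scored at each screen, so preventing new use counts. One or two negative qualitative dipsticks also do not prove that illicit use has stopped.
- *Imbalance in the share of co-users would pass for a drug effect.* Randomisation keeps the comparison unbiased, the type I error is unaffected (step 5), and section 7c has a covariate rule for baseline differences in use. That rule is conditional and loosely worded. It addresses imbalance but not dilution or interpretation.
- *The primary opioid test should be confined to baseline-positive patients.* That discards randomised participants with no gain of note over adjustment, and with a clear loss if the drug also prevents new use (step 4).

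It is also fair to say that the size rests on assumptions. The plan gives no entry-positive share, and the linear shrinkage in step 2 applies to risk differences. The conditional odds ratio from a random-intercept logistic model need not shrink in proportion.

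**Conclusion.** The concern holds as a matter of efficiency and interpretation, not validity. Nothing in eligibility ensures that participants are using non-prescribed opioids, and nothing in section 7c guarantees that opioid status at entry is used for the urine and craving outcomes.

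Under the assumed rates, with half the sample negative at entry, an analysis that ignores baseline has 34% power on person means, or 44% in the mixed logistic model. Adjustment for entry status has about 64–69% and 82% respectively. If baseline turns out to be a modelled timepoint and the effect is read from the interaction, most of the power problem disappears, but the difficulty of interpreting a null result remains. The true loss is unknown because q is unknown. Floor effects on opioid craving and cue reactivity are possible, but no figure in the documents shows them. The change is worth making because it uses data already collected.

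**What to change.** In section 7c:

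1. For the Aim 1 opioid outcomes, replace the conditional covariate rule with unconditional inclusion of baseline opioid status, defined as any non-prescribed-opioid-positive urine at screening or randomisation, before the first dose. Keep all randomised participants in the primary analysis. State whether baseline is also a modelled timepoint, so that the same screen does not serve as both covariate and outcome.
2. Before unblinding, pre-specify a supportive analysis of opioid use and craving in the baseline opioid-positive (co-use) set. Report baseline-negative participants separately as maintenance of opioid-negative status.
3. Base any statement about reducing opioid use among active opioid/stimulant co-users on that set. The cocaine outcomes stay on everyone.

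The cost is wording and one extra model term, with no new data and no change to eligibility or treatment. The supportive set will be small and imprecise: 20 × 0.3 = 6 to 20 × 0.6 = 12 per arm if 30–60% are baseline-positive, which is an assumption. If no baseline-negative participant ever tests positive, the covariate's coefficient will not have a finite maximum likelihood estimate, so a penalised fit should be named in advance as the fallback.
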